#### **9.1.4. Follow-up Phase**

The Follow-up Phase will consist of 2 phases: a Post-treatment Pre-disease Progression Phase and a Post-disease Progression Phase.

##### **9.1.4.1. Post-treatment Pre-disease Progression Phase**

Subjects who discontinue the treatment for reasons other than PD will be followed every 12 weeks ( $\pm 7$  days) by clinic visit until disease progression is confirmed, regardless of initiation of subsequent anticancer treatment. Procedures performed during this period are outlined in [TIME AND EVENTS SCHEDULE](#).

##### **9.1.4.2. Post-disease Progression Phase**

After investigator confirmed disease progression, subjects will be contacted to assess survival status, the use of alternative antineoplastic therapy and occurrence of any other malignancy approximately every 12 weeks ( $\pm 7$  days) by clinic visit or telephone until death, withdrawal by subject, lost to follow-up, or study terminated by Sponsor, whichever comes first. At the time of the primary analysis and at study closure, a survival sweep will be conducted. All subjects who are on study and not known to have died prior to the survival sweep will be contacted at that time.

#### **9.1.5. Clinical Cut-offs**

Clinical cutoffs (CCOs) planned for this study are:

- CCO for the primary analysis is estimated to be performed approximately 12 months after the last subject receives first dose. Alternative appropriate cutoffs will be considered based on regulatory requirement.
- CCO for the final analysis is estimated to occur 3 years after last subject receives first dose.

#### **9.2. Efficacy Evaluations**

Efficacy evaluations will be conducted as outlined in the [TIME AND EVENTS SCHEDULE](#). Response assessments will be performed using the modified consensus criteria adapted from the VIth IWWM (NCCN 2019) ([Attachment 1](#)).

Progression of nodal and extranodal disease should be evaluated based on the revised criteria for malignant lymphoma described in the revised International Working Group for NHL.

Efficacy evaluation will include the following components:

- Hematologic parameters by complete blood count (CBC)
- Quantitative IgM serum immunoglobulins

- Quantitative serum-M protein (serum protein electrophoresis [SPEP])
- Serum free light chain assay
- Qualitative serum immunofixation, if applicable
- Radiographic evaluation, if applicable
- Bone marrow aspirate and biopsy, if applicable

Sequential changes in IgM levels used for assessing responses can be determined either by SPEP or by quantitative IgM serum immunoglobulins. It is crucial that for each subject, sequential response assessments are performed using the same methodology which is prespecified by site.

In the event a subject required plasmapheresis prior study treatment, the IgM level obtained prior plasmapheresis will be considered as the baseline value and study treatment should be initiated shortly thereafter (not more than 7 days) after last plasmapheresis. IgM level obtained within five half-lives (ie,  $\leq 35$  days) after plasmapheresis should not be considered as nadir on therapy or for response evaluation. IgM levels obtained more than 35 days after plasmapheresis can be used in response determination.

Any suspected case of disease progression should be reported to the Sponsor within 24 hours of awareness. If disease progression is suspected solely based on the results of a single examination or a single laboratory parameter (eg, IgM), this finding should be confirmed by a subsequent evaluation at least within 4 weeks from the first finding. Additional hematologic parameters, radiographic evaluation and bone marrow aspirate and biopsy should be performed at the discretion of the treating physician to confirm progressive disease if indicated.

In general, subjects should continue study treatment until progression is confirmed by a serial examination within 4 weeks from the first finding. When disease progression has been confirmed, study treatment should be withheld. Once disease progression has been confirmed, subjects should continue to adhere to all other study-related procedures. Whenever possible, subsequent anticancer therapy should be withheld until disease progression is confirmed.

If at any time complete response (CR) is suspected (serum IgM values in normal range and disappearance of the SPEP), all assessments including serum immunofixation, bone marrow assessment and radiographic evaluation (if nodal/extranodal disease is present at baseline) must be performed according to the IWWM response assessment guidelines.

### **9.2.1. Quantitative Serum Immunoglobulin**

Testing for IgA, IgG and IgM levels will be performed by a central laboratory.

### **9.2.2. Serum Protein Electrophoresis (SPEP)**

Sample(s) will be sent to a central laboratory to quantify the serum-M protein.

### **9.2.3. Serum Free Light Chain Assay**

Sample(s) will be sent to a central laboratory for measurement of immunoglobulin-free light chains in serum.

## **9.2.4. Serum Immunofixation**

Samples will be collected and sent to a central laboratory. Repetitive immunofixation on study is only required to confirm CR (conducted on the first observation that the subject has no detectable monoclonal protein) and then repeated every study visit until disease progression.

## **9.2.5. Radiographic Imaging**

Pretreatment tumor assessment will be performed up to 42 days before the first dose of study drug. Lesions that have been irradiated cannot be included in the tumor assessment unless unequivocal tumor progression has been documented in these lesions after radiation therapy.

A computed tomography (CT) scan (with contrast unless contraindicated) of the neck, chest, abdomen, and pelvis must be performed. Information on extranodal involvement will also be recorded.

Magnetic resonance imaging (MRI) is only allowed to evaluate sites of disease that cannot be adequately imaged using CT or in the case where CT with contrast is contraindicated (in cases where MRI is desirable, the MRI must be obtained at baseline and at all subsequent response evaluations). If MRI is required for any other reason, this must be discussed with the study medical monitor first.

The same imaging method should be used for a given subject throughout the study. The same equipment should be utilized for all scans whenever possible. The same radiologist should be assigned to read all the scans for a given patient throughout the study as much as possible.

All subjects with presence of nodal and/or extranodal disease at Screening will require follow up CT scans of the neck, chest, abdomen, and pelvis every 16 weeks for the first 2 years and thereafter every 24 weeks, until disease progression is confirmed (regardless of whether or not the subject remains on treatment). In the event disease progression is suspected due to physical examination or laboratory test, a CT scan should be performed to evaluate nodal or extranodal progression regardless if the subject had nodal/extranodal disease at Screening.

### **9.2.5.1. Radiographic Assessment**

Progression of nodal and extranodal disease should be evaluated based on the revised criteria for malignant lymphoma described in the revised International Working Group for NHL. The spleen is considered nodal disease.

Up to 6 measurable lymph nodes should be considered as target lesions if the long axis is more than 1.5 cm regardless of the short axis. If a lymph node has a long axis of 1.1 to 1.5 cm, it should only be considered abnormal if its short axis is more than 1.0 cm. Lymph nodes  $\leq 1.0$  cm  $\times \leq 1.0$  cm will not be considered as abnormal for relapse or progressive disease. In addition, target lesions should be clearly measurable in at least 2 perpendicular dimensions and, if possible, they should be from disparate regions of the body when these areas are significantly involved. If additional lesions are present but are not included in the target lesion assessment, they can be added as non-target lesions followed throughout the study.

The longest cranial-caudal measurement of the spleen will be assessed at Screening and all subsequent timepoints (if applicable). Splenomegaly is present when the cranial to caudal measurement of the spleen is >130 mm.

Nodal progression by imaging is defined as one of the following:

- Appearance of any new lesion more than 1.5 cm in any axis during or at the end of therapy, even if other lesions are decreasing in size.
- At least a 50% increase from nadir in the sum of product (SPD) of any previously involved nodes, or in a single involved node. To be considered progressive disease, a lymph node with a diameter of the short axis of less than 1.0 cm must increase by  $\geq 50\%$  and to a size of  $1.5 \times 1.5$  cm or more than 1.5 cm in the long axis.
- At least a 50% increase in the longest diameter of any single previously identified node more than 1 cm in its short axis.

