- d. Only a limited symptom-directed physical examination and the change in status of lymph nodes, tumor masses, liver and spleen will be required. Review of symptoms should include inquiry of ocular symptoms; subjects should be referred to an ophthalmologist for a formal examination if any Grade  $\geq 2$  symptoms are reported.
- e. Women of reproductive potential only. Serum pregnancy test required at Screening. During the trial, if the subject is suspected of pregnancy, pregnancy test must be performed. Pregnancy test will be done by the local laboratory.

- f. Serum viscosity at Screening is optional. Subsequent serum viscosity (after Screening) should be performed at the discretion of the treating physician in any subject with signs and symptoms suggesting a hyperviscosity syndrome.
- g. Repetitive serum immunofixation on study is only required to confirm CR (conducted on the first observation that the subject has no detectable monoclonal protein) and then repeat every time until disease progression.
- h. Predose PK samples will be drawn for all subjects according to the schedule in Section 9.3.1.
- i. CT scans of the neck, chest, abdomen, and pelvis should be obtained during Screening (up to 42 days before first dose) for each subject.
- j. Follow-Up CT scans will be required at Weeks 17, 33, 49 65, 81, 97 and thereafter every 24 weeks until PD is confirmed for all subjects with measurable nodal/extranodal disease during Screening. Additional assessments may be performed if clinically indicated during the course of the study at any time.
- k. CT scan at Suspected PD visit may be performed if clinically indicated as a reason for progression.
- l. Bone marrow aspirate and biopsy required at Screening, Weeks 49 and 97 ( $\pm$  2 weeks) to confirm paraprotein changes, and at any time as determined necessary or to confirm a complete response if the subject has no detectable monoclonal protein, and if clinically indicated at disease progression or EOT visit.
- m. The assessments can be performed via a clinical visit or a telephone contact.
- n. To be done predose, unless otherwise specified. Hematology and serum chemistry tests do not need to be repeated if the screening tests were performed within 5 days of the first dose of study drug.

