Progressive Disease (PD)	
At least one of the following
 
 
A <math>\geq 25\%</math> increase in serum IgM with a total increase of at least 500 mg/dL from nadir 
 
Confirmation of the initial IgM increase is required when IgM is sole criterion for progressive disease.
 
 
 
Appearance of a new lymph nodes <math>>1.5</math> cm in any axis, <math>\geq 50\%</math> increase from nadir in sum of product of diameters (SPD) of more than one node, or <math>\geq 50\%</math> increase in longest diameter of a previously identified node <math>>1</math> cm in short axis
 
Appearance of new splenomegaly or <math>\geq 50\%</math> increase from nadir in enlargement of the spleen
 
Appearance of new extranodal disease2/3
 
New or recurrent involvement in the bone marrow
 
New symptomatic disease on the basis of malignant pleural effusion, Bing Neel (WM CNS disease) syndrome, amyloidosis or light chain deposition disease, or other paraprotein mediated disorder.
 

Abbreviations: CNS= central nervous system; WM= Waldenström's macroglobulinemia

1. Nadir for serum IgM is defined as the lowest serum IgM value obtained at any time from baseline onwards with the exception that serum IgM levels post-plasmapheresis will not be considered for up to 35 days.
2. For additional clarification to assess the appearance or progression of existing nodal and extranodal disease (Refer to Section 9.2.5)
3. Measurable extranodal disease should be assessed in a manner similar to that for nodal disease.
4. Sum of the products of multiple lymph nodes (as evaluated by CT scans) or the longest diameter of one target lymph node.

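### Protocol Section 9.2.5.1 and Attachment 1 differ on whether a new node first seen after treatment has ended is progression, so a PFS or DOR event could be missed or dated late

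*Protocol*

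**What the plan says.** - **Protocol Section 9.2.5.1.** Three bullets follow the words "Nodal progression by imaging is defined as one of the following". The first is "Appearance of any new lesion more than 1.5 cm in any axis during or at the end of therapy", and it applies even when other lesions are shrinking. The other two concern growth of nodes already known and carry no timing.
- **Protocol Attachment 1, progressive disease row.** It lists "Appearance of a new lymph nodes" above 1.5 cm in any axis, with no reference to treatment. Footnote 2 on that row reads "For additional clarification to assess the appearance or progression of existing nodal and extranodal disease (Refer to Section 9.2.5".
- **Protocol Section 9.2.5.** Subjects with nodal or extranodal disease at Screening have CT every 16 weeks for two years and every 24 weeks after that, "until disease progression is confirmed (regardless of whether or not the subject remains on treatment". Footnote j of the Time and Events Schedule, which is also attached to the post-treatment pre-progression column, says "thereafter every 24 weeks until PD is confirmed for all subjects with measurable nodal/extranodal disease during Screening".
- **Protocol Section 9.1.4.1.** Subjects who stop drug without progression are seen every 12 weeks "by clinic visit until disease progression is confirmed, regardless of initiation of subsequent anticancer treatment".
- **Endpoint rules.** PFS (Protocol Section 11.3.2.5) runs from first dose to progression or death, with no on-treatment limit. SAP Table 2 counts progression or death for PFS and DOR whether or not other antineoplastic therapy came first. It censors a subject not known to have progressed or died at the last adequate assessment without progression.

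**The concern.** The scans taken after study drug stops are there to date progression. On a literal reading of the Section 9.2.5.1 list, regrowth of a known node on such a scan is nodal progression, but a new node on the same scan is not. Attachment 1 would call both progression. Response and progression are assessed by investigators at several sites, so two sites could code the same scan differently.

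If the new node is not counted, SAP Table 2 either leaves the subject censored as progression-free or takes the event date from a later finding. Both lengthen PFS and DOR. The study has about 17 subjects, the protocol names DOR as a key secondary endpoint (Section 3.2.2), PFS is reported at 1, 2 and 3 years, and the data are meant to support full approval in China (Section 1.2).

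**Working it through.** **1. The plan's own figure.** The documents give no figure on this point. The nearest is the power of the primary test (Protocol Section 11.2): n = 17, ORR 69.8% against 32%, one-sided 0.05, power at least 85%. By the exact binomial, the smallest number of responders whose Clopper-Pearson lower limit exceeds 0.32 is 10 (10/17 gives 0.364; 9/17 gives 0.311). Then P(X ≥ 10 | 0.32) = 0.0204 and P(X ≥ 10 | 0.698) = 0.892, so the claim is met. No input to this calculation uses the progression rule.

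**2. The two texts side by side, read literally.**

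| Finding on CT | Section 9.2.5.1 list | Attachment 1 |
|---|---|---|
| New node above 1.5 cm, during treatment or at its end | Progression | Progression |
| New node above 1.5 cm, first seen after treatment has ended | Not on the list | Progression |
| Longest diameter of a known node (short axis above 1 cm) up by 50% or more, at any time | Progression | Progression |

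**3. Which text governs.** The documents state no order of precedence. Footnote 2 of Attachment 1 sends the reader to Section 9.2.5. That section contains both the instruction to keep scanning off treatment and, in 9.2.5.1, the bullet with the timing phrase, so the footnote does not settle the matter.

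**4. Who could be affected.** All of the following must hold:
- the subject stops drug without progression;
- the subject had nodal or extranodal disease at Screening (and so has scheduled CT), or has an unscheduled scan;
- a new node is the first sign, with no other criterion met;
- the assessor follows the 9.2.5.1 list rather than Attachment 1.

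The documents give no rate for any of these. If 2 to 4 of 17 (12% to 24%, an assumption) met the first condition, the number meeting all four would lie between zero and that figure.

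**5. Size per event.** With no censoring before the landmark, S(t) = 1 − d/17, where d is the number of events. One event fewer adds 1/17 = 5.9 percentage points, and two add 2/17 = 11.8.

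A Kaplan-Meier illustration uses assumed event times:
- PFS: 17 subjects, progression at months 6, 12, 15, 20, 24 and 30, the rest event-free to month 36. The uncounted events are those at month 12, then months 12 and 15.
- DOR: 12 responders (0.698 × 17 = 11.9), progression at months 8, 13, 18 and 26, the rest event-free to month 36. The uncounted events are those at month 13, then months 13 and 18.

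An uncounted subject is either (a) followed as event-free to month 36 or (b) censored 3.7 months (16 weeks) before the event.

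| Estimate | 0 uncounted | 1 uncounted (a) / (b) | 2 uncounted (a) / (b) |
|---|---|---|---|
| PFS, 24 months | 70.6% | 76.5% / 75.3% | 82.4% / 80.7% |
| PFS, 36 months | 64.7% | 70.6% / 69.0% | 76.5% / 73.9% |
| DOR, 24 months | 75.0% | 83.3% / 82.5% | 91.7% / 91.7% |

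For example, 24-month PFS with one uncounted event under (b) is 16/17 × 12/15 = 0.753, against 12/17 = 0.706 with all events counted. In this scenario each uncounted event adds about 5 to 6 points to 24-month PFS and about 8 points to 24-month DOR. If no such event occurs, the effect is zero.

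**The case against.** The bullet does not say *only*. It goes on to say that a new lesion counts even when others shrink, so its purpose looks inclusive, and the neighbouring bullets carry no timing. PFS is defined by the modified workshop criteria, which Attachment 1 sets out for the investigator. Footnote 2 points to the whole of Section 9.2.5, which orders scans off treatment. An investigator reading such a scan is unlikely to disregard a new node, and Section 9.2 requires suspected progression to be reported to the sponsor within 24 hours, which may expose differences between sites.

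Much of this stands. It makes the exclusionary reading less likely in practice. It does not remove the conflict, because Section 9.2.5.1 presents its list as a definition and no text says that Attachment 1 prevails. Nor can the node be set aside as relapse rather than progression: Attachment 1 has no relapse category, and PFS and DOR events are progression or death.

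A reader might also infer that a missed event must wait for the next scheduled CT, 16 to 24 weeks on. The documents do not support that. IgM, SPEP, physical examination and overall disease assessment take place every 12 weeks after treatment. CT may be done at any time if clinically indicated, and should be done when examination or laboratory results suggest progression. The IgM, known-node, spleen, marrow, extranodal and symptomatic criteria in Attachment 1 have no treatment-time limit.

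**Conclusion.** On a literal reading, the two passages give different answers for a new node first seen after treatment has ended, and they should be reconciled. It would go too far to conclude that PFS and DOR will be overstated. An assessor using Attachment 1 counts the event, other criteria may capture it, and the number of subjects who meet all the conditions is unknown and may be zero. If an event is left uncounted, the bias is upward: about 5.9 points on a PFS landmark per event, assuming 17 subjects and no earlier censoring. The larger DOR shift rests on the assumed 12 responders and assumed event times. Only secondary, descriptive endpoints are touched. The primary ORR test and the sample size are unaffected. This is a minor point, worth correcting because the correction is so small.

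**What to change.** In the first bullet of Protocol Section 9.2.5.1, delete the timing phrase that closes the quoted words. Alternatively, state that the new-lesion criterion applies at any assessment from baseline until progression, on or off study drug. Either way, one new-lesion rule then covers the whole period over which PFS and DOR are followed, in line with Attachment 1, Section 9.2.5 and SAP Table 2.

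The cost is a few words in the next protocol amendment, with no extra scan, visit or reader. The subjects concerned are already off study drug, so dosing does not change.

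The deletion does not make the two texts identical. Section 9.2.5.1 speaks of lesions where Attachment 1 speaks of lymph nodes. It also accepts a 50% rise in the product of diameters in a single involved node, where Attachment 1 asks for more than one node. Those differences can be checked in the same edit.

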### **9.2.6. Bone Marrow Assessment and Pathological diagnosis**

Bone marrow aspirate and biopsy is required at Screening. Inclusion of the subject in the trial will be based on central pathological assessment and histopathological confirmation of lymphoplasmacytic lymphoma (LPL), which is the underlying histology of WM.

Additional Bone Marrow assessment should be obtained:

- to confirm CR at any time
- predose at Weeks 49 and 97 to assess bone marrow/tissue response
- at time of progression or at suspected PD due to progressive cytopenia without any other evidence of PD

Standard clinical Bone Marrow assessment will all be performed at the central laboratory.

## **9.3. Pharmacokinetics**

### **9.3.1. Evaluations**

Venous blood samples of approximately 2 mL will be collected from all subjects for measurement of plasma concentrations of ibrutinib and metabolite PCI-45227 before dosing ibrutinib capsules on Day 1 of Weeks 1, 5, and 9 (see [TIME AND EVENTS SCHEDULE](#)).

Subjects should refrain from taking the study drug on the morning of study visits designated for PK sampling. After PK sampling, the study drug will be self-administered by the subjects on an outpatient basis, except for Day 1 of Week 1, when the study drug will be administered in the clinic. The exact dose, dates and times for the doses administered 1 day preceding and actual PK sampling dates and times must be recorded. Additional information about the collection, handling, and shipment of biological samples can be found in the Laboratory Manual.

Samples collected for PK analyses may additionally be used to evaluate safety or efficacy aspects that address concerns arising during or after the study period.

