### **1.1.2.1. Human Pharmacokinetics**

The PK of ibrutinib has been assessed in subjects with B-cell malignancies, cGVHD, as well as in healthy subjects. In all studies, both parent ibrutinib and metabolite PCI-45227 were quantified. PCI-45227 is a prominent dihydrodiol metabolite observed in laboratory animals and humans, with a reversible inhibitory activity towards BTK approximately 15 times lower than that of ibrutinib and with plasma concentrations in the same range as parent drug levels. The on target effects of metabolite PCI-45227 are not considered clinically relevant. The PK of ibrutinib does not significantly differ in patients with different B-cell malignancies (CLL, SLL, MCL, WM, and MZL). Ibrutinib is absorbed after oral administration with a median  $T_{max}$  of 1 hour to 2 hours. The half-life of ibrutinib is 4 to 6 hours. Administration of ibrutinib in a fasted condition resulted in approximately 60% of exposure (AUC) as compared to administration either in fed condition (30 minutes after a high-fat breakfast), or 2 hours after a meal. Considering the approximate doubling in mean systemic exposure when dosed with food and the favorable safety profile, ibrutinib can be dosed with or without food. The PK in Chinese CLL/SLL patients is similar to those in non-Chinese subjects with various B-cell malignancies.

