#### **6. DOSAGE AND ADMINISTRATION**

Ibrutinib will be administered orally, once daily, at a dose of 420 mg (140 mg × 3 capsules taken together at one time). Protocol-specified dose modifications of ibrutinib will be made as

necessary. Study drug (3 capsules) is administered orally once daily with approximately 8 ounces (240 mL) of water. The capsules should be swallowed whole and should not be opened, broken, or chewed. The use of strong CYP3A inhibitors/inducers, and grapefruit and Seville oranges should be avoided for the duration of the study (Section 8.2 and Attachment 3).

If a dose is not taken at the scheduled time, it can be taken as soon as possible on the same day with a return to the normal schedule the following day. The subject should not take extra capsules to make up the missed dose. Missed doses of study drug will not be made up.

The first dose will be administered in the clinic on Day 1 of Week 1, after which study drug will be self-administered daily by the subjects on an outpatient basis. Study drug will be dispensed to subjects in bottles. Unused study drug dispensed during previous visits must be returned to the site and drug accountability records (Section 14.5) updated at each visit. Returned capsules must not be re-dispensed to anyone.

Study drug dosing is continuous (without interruptions) throughout the Treatment Phase.

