## 11.4. Pharmacokinetic Analyses

The plasma concentration data for ibrutinib and metabolite PCI-45227 at each timepoint will be listed and summarized using descriptive statistics. All concentrations below the lowest quantifiable concentration or missing data will be labeled as such in the concentration data listing. Concentrations below the lowest quantifiable concentration will be treated as zero for the population PK modeling, if needed. All subjects and samples excluded from the analysis will be clearly documented in the study report.

If feasible, population PK analysis of ibrutinib may be performed using nonlinear mixed-effects modeling (NONMEM). Data may be pooled with other ibrutinib trials if appropriate. Model-derived exposure parameters may be subjected to further explore correlation between exposure and relevant clinical information.

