## 7. PHARMACOKINETICS

Pharmacokinetic evaluable analysis set will be used for PK analyses. The individual plasma concentration data of ibrutinib and its metabolite PCI-45227 will be listed and graphically displayed (linear scale and/or semi-log scale). Concentrations below the lowest quantifiable concentration or missing data will be labeled as such in the concentration data presentation. The data will be summarized at each timepoint using descriptive statistics (mean, standard deviation [SD], coefficient of variation, median, minimum and maximum) and will be graphically displayed if possible. Concentration data below the lowest quantifiable concentration will be treated as zero in the summary statistics.

Subgroup analysis by ibrutinib dose and concomitant CYP3A inhibitors may be performed on the individual pre-dose plasma concentration at Week 5 Day 1 and Week 9 Day 1 of ibrutinib and PCI-45227. Necessity of subgroup analysis will be determined based on the actual number of subjects who received concomitant CYP3A inhibitors and/or dose reduction till the pre-dose of Week 9 Day 1. Summary tables and visual comparisons may be provided to present the summary statistics derived for each subgroup, if possible. The visual comparisons graphical presentation may also be performed for dose-normalized pre-dose plasma concentration of ibrutinib at Week 5 Day 1 and Week 9 Day 1 regardless of ibrutinib dose.

Additional analyses may be performed as deemed necessary.

Based on the individual plasma concentration-time data, using the actual dose taken and the actual sampling times, PK parameters and exposure information of ibrutinib may be derived using population PK modelling, if it is deemed appropriate and if data allow.

For concentration summary, applying the following rules.

- When more than half (>50%) of concentration data are BQL at each scheduled time point, mean and median will be reported as 'BQL'; SD and %CV are reported as 'NC'; maximum and minimum will be reported as observed (including BQL).
- When number of concentration data are equal to or less than 2, SD, %CV, median, minimum and maximum will be shown as 'NC' regardless of the proportion of BQL.

Data or subjects will be excluded from the analysis if the data do not allow for accurate assessment of the PK. All subjects and samples excluded from the analysis will be clearly documented in the study report.

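### The Week 5 and Week 9 predose ibrutinib summaries ignore time since the last dose, so samples taken well under 24 hours after a dose may be averaged with 24-hour troughs

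*Protocol*

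**What the plan says.** Protocol 6 sets the regimen: "Ibrutinib will be administered orally, once daily, at a dose of 420 mg". No clock time is given. The section refers to a scheduled time without defining it, and adds: "If a dose is not taken at the scheduled time, it can be taken as soon as possible on the same day". After the first dose, subjects take the capsules at home.

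Under Protocol 9.3.1, samples are drawn "before dosing ibrutinib capsules on Day 1 of Weeks 1, 5, and 9". For those visits, "Subjects should refrain from taking the study drug on the morning of study visits designated for PK sampling". No minimum or target interval since the previous dose is stated. The section does require the dose, date and time of the previous day's dosing, and the actual sampling time, to be recorded.

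For the analysis, Protocol 11.4 says that the concentrations "at each timepoint will be listed and summarized using descriptive statistics", and SAP 7 says "The data will be summarized at each timepoint using descriptive statistics": mean, SD, coefficient of variation, median, minimum and maximum. SAP 2.1 assigns visits as recorded on the CRF. The possible PK subgroups in SAP 7 are by ibrutinib dose and CYP3A inhibitor use. Actual dose and sampling times enter only the population PK model, which is optional.

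**The concern.** A predose label does not fix the time since the last dose. A subject who doses in the morning and holds that day's dose is sampled about 24 hours after the previous one. A subject who doses in the evening follows every instruction and is sampled perhaps 12 to 15 hours after a dose. A subject who missed the previous day is sampled about 48 hours after. All three fall under one timepoint in the summary.

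The half-life is short relative to these gaps, so elapsed time can move a concentration by a large factor. PK in Chinese subjects is a secondary objective. If intervals do differ, part of the reported level and spread would reflect when capsules were taken and not how the drug is handled. A reader of the summary table could not separate the two.

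**Working it through.** The documents give no expected concentration or PK precision figure, so there is none to reproduce.

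**Inputs from the documents**
- Protocol 1.1.2.1: "The half-life of ibrutinib is 4 to 6 hours". Median Tmax is "of 1 hour to 2 hours".
- Protocol 6: once-daily dosing, so the trough interval is 24 hours.
- Protocol 3.1: approximately 17 subjects.
- Week 1 precedes the first dose, so only Weeks 5 and 9 are concerned.

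**Assumptions**
- Concentrations decline mono-exponentially at the stated half-life h.
- All subjects have identical PK, so any difference is due to timing alone.
- m of 17 subjects are sampled early, with m = 2 to 4. The documents give no number.

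**Step 1: ratio of an early sample to a 24-hour sample.** For a sample at t hours, R = 2^((24 − t)/h).

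| Half-life | 12 h sample | 15 h sample |
|---|---|---|
| 6 h | 2^(12/6) = 4.0 | 2^(9/6) = 2.8 |
| 5 h | 2^(12/5) = 5.3 | 2^(9/5) = 3.5 |
| 4 h | 2^(12/4) = 8.0 | 2^(9/4) = 4.8 |

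A one-compartment steady-state model with absorption set to a Tmax of 1 or 2 hours leaves the 12-hour ratios unchanged to the precision shown.

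**Step 2: effect on the mean.** Mean relative to an all-24-hour group = (17 − m + mR)/17. With early samples at 12 hours:

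| Half-life | m = 2 | m = 4 |
|---|---|---|
| 6 h | (15 + 8)/17 = 1.35 | (13 + 16)/17 = 1.71 |
| 5 h | (15 + 10.6)/17 = 1.50 | (13 + 21.1)/17 = 2.01 |
| 4 h | (15 + 16)/17 = 1.82 | (13 + 32)/17 = 2.65 |

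With early samples at 15 hours the range is smaller: (15 + 2 × 2.83)/17 = 1.22 to (13 + 4 × 4.76)/17 = 1.88.

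**Step 3: effect on the spread.** Timing alone gives SD² = m(17 − m)(R − 1)²/(17 × 16). For m = 4 and R = 4, SD = 1.31 and CV = 1.31/1.71 = 77%. For m = 4 and R = 8, SD = 3.06 and CV = 3.06/2.65 = 116%. The maximum rises by the factor R. The median, the ninth of 17 ordered values, stays at the 24-hour level in this timing-only model when m is 2 to 4.

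**Step 4: effect of a time window.** Between 22 and 26 hours after a dose, the largest timing-only ratio is 2^(4/6) = 1.6 to 2^(4/4) = 2.0. Between 20 and 28 hours it is 2^(8/6) = 2.5 to 2^(8/4) = 4.0.

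**The case against.** The strongest reply is that nothing in the documents shows that anyone doses in the evening. The first dose is given in clinic, the PK-day instruction concerns the morning dose, and self-administration follows the sample. That wording fits morning dosing. A reader might infer that 12-hour and 24-hour samples are in fact averaged together, or that dosing habit dominates the mean. The documents do not support either statement: they allow the mixture but do not establish it. If everyone doses in the morning, only the spread around 24 hours remains. This part of the reply stands, and the point is conditional for that reason.

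A reader might also infer that the by-visit summary is the only PK output the plan commits to. It is not: SAP 7 also commits to listing and graphing individual concentrations. The median is reported, and when more than 50% of values at a timepoint are below the quantification limit, neither mean nor median is shown. The limit is not given, so how often that rule applies is unknown. The plan states no PK hypothesis, acceptance criterion or planned comparison of trough means with other populations.

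Three other replies carry less weight:
- Population PK would use actual times, but it is optional.
- Data that do not permit accurate PK assessment may be excluded, but no time-since-dose criterion is named. One chosen after the concentrations are seen would be post hoc.
- Recording the times makes a correction possible, but the committed summary does not use them.

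**Conclusion.** The point holds as a minor, conditional improvement to SAP 7. The protocol permits unequal intervals before the Week 5 and Week 9 samples, and the summary takes no account of them. For ibrutinib, an early sample could be 2.8 to 4.8 times (15 hours) or 4 to 8 times (12 hours) a 24-hour value. With 2 to 4 of 17 subjects sampled at 12 hours, the mean would be 1.35 to 2.65 times the 24-hour value. The SD, CV and maximum would be affected too; the median much less.

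The ratios rest on the stated half-life and mono-exponential decline, the effect on the mean also on an assumed number of early samples. They do not apply to PCI-45227, for which no half-life is given. A reader might extend the point to the trial's conclusions, but the response rate and the safety analyses do not use these concentrations.

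**What to change.** Change SAP 7 only; dosing, visits and samples stay as they are.

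1. Derive time since last dose for each Week 5 and Week 9 sample from the dose and sampling times that Protocol 9.3.1 already requires.
2. List and plot the individual concentrations against that time.
3. Base the trough summary on samples within a prespecified, justified window around 24 hours after a dose taken the day before. For example, 22 to 26 hours limits the timing-only ratio to 1.6 to 2.0. A window of 20 to 28 hours would readmit a 2.5- to 4-fold spread.
4. Keep the all-sample summary alongside, and list out-of-window samples with their elapsed time.

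The cost is one derived variable, some SAP wording and a smaller n in the trough table. Under the assumption above, 2 to 4 of 17 subjects would drop out of it, leaving 13 to 15. Missed doses or morning intervals outside the window would reduce it further. Keeping the all-sample summary means that no data are lost from the report.
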